- The expected seroconversion rates that were used for the sample size calculation were retrieved from published data of patients with a CD4-count of 200-350 cells/mm^2. However, 92% of the patients that are currently included have a CD4-count of  $> 350$  cells/mm^2, which makes seroconversion rates in patients with more than 350 CD4+ cells/mm^2 more applicable (1). Published seroconversion rates in these patients are 95%-99% for HPV types 6, 11 and 16 and 90% for HPV-18.
- This sample size calculation does not take in to account that patients might be seropositive to certain HPV-types at baseline and that their data will be excluded for the analysis of the seroconversion outcome of the corresponding HPV-type. Seroprevalence to different HPV-types in previous studies on the safety and immunogenicity of the quadrivalent HPV-vaccine in HIV patients ranged from 13% to 45% for the different vaccine HPV-types (1-3).
- In order to maximize the number of eligible subjects, we amend the protocol to also **include patients with a history of abnormal PAP-smears without treatment or genital warts**. We believe that this allows us to reach a total sample size of at least 100 HIV-patients. Patients who are seropositive for a given HPV-type at baseline will

still be excluded for the analysis of seroconversion of that particular type but will still be useful for the analysis of the other HPV-types. Knowing that in HIV-patients the expected seroconversion rate of HPV-18 is relatively lower than the seroconversion rates of HPV types 6, 11 and 16, maximizing the number of eligible subjects for the analysis of this type is especially beneficial in order to obtain a reasonable margin of error. Enrolling patients with history of genital warts, who are most likely seropositive to HPV types 6 or 11, still allows us to increase the number of HPV-18 seronegative patients. In addition, clinical presentation of HPV infection does not necessarily implicate seropositivity to HPV.

- **With a total sample size of n=100, a majority of whom will have no history of HPV-lesions, we expect to be able to use the data of at least 80 patients for the analysis seroconversion of each HPV type under study. Seroconversion rates of 95-99% for HPV types 6, 11 and 16 can then be estimated with a margin of error of  $\pm 4.8\%$  -  $2.2\%$ , and the anticipated seroconversion rate of 90% for HPV type 18 with a margin of error of  $\pm 6.6\%$ .**

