### 3.5.4 Analysis Populations

#### 3.5.4.1 Immunogenicity Analysis Populations

##### Per Protocol Immunogenicity Population

The per-protocol immunogenicity (PPI) analysis populations will serve as the primary populations of subjects for the analysis of immune responses to each of the 9 HPV types (6, 11, 16, 18, 31, 33, 45, 52, and 58). The PPI analysis populations are HPV type-specific, i.e., each HPV type has its own PPI analysis population. To be included in a particular HPV type-specific PPI analysis population, subjects must:

- Have received all 3 vaccinations of the correct dose of GARDASIL®9 within acceptable day ranges (See Table 4).
- Have evaluable serology results at Day 1 and Month 7 based on serum samples collected within acceptable day ranges (See Table 5).
- Be seronegative to the appropriate HPV type at Day 1.
- Have no protocol deviations that could interfere with the evaluation of subject's immune response to GARDASIL®9.

To be included in the PPI analysis population for any vaccine HPV type, subjects need to be seronegative to that specific type at Day 1. The final determination of protocol deviation categories deemed as having potential to interfere with evaluation of immune response to GARDASIL®9 will be made prior to database lock and will be recorded in a separate study document.

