### **3.5.5 Statistical Methods**

#### **3.5.5.1 Immunogenicity Analyses**

The primary analyses of immunogenicity will be conducted in the Per Protocol Immunogenicity (PPI) population as defined in Section 3.5.4.1. Immunogenicity data will be analysed separately for HIV and SOT patients. The potential influence of factors such as immunosuppressive therapy and time after transplantation for SOT patients and CD4-count and antiretroviral therapy for HIV patients will be estimated.

- Seroconversion

The primary outcome, seroconversion, defined as changing serostatus from seronegative at Day 1 to seropositive (antibody titre above seroconversion cut-off) by 4 weeks after Dose 3, will be described with 95% CI. Differences with historical controls will be determined with a test for binary (seroconversion or not) proportions.

- GMT

All titers will be log transformed and the antilog of the mean will be calculated to obtain the GMT. GMT will be described with 95%CI. GMTs of immunocompromised patients will be compared with GMTs of historical controls with a one sample *t*-test, comparing month 7 GMTs for each component.

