### **3.5.6 Sample Size and Power Calculations**

Based on an expected seroconversion rate of 80%, a sample size of 170 transplant patients allows to estimate the proportion of protected transplant patients with precision (95% confidence interval) of  $\pm 6\%$  (10).

Furthermore, based on an expected seroconversion rate 85-91%, a sample size of 140 HIV-patients allows to estimate the proportion of protected patients with precision (95% confidence interval) of  $\pm 6\%$  and 5% respectively (7). Based on expected differences in GMT to healthy populations, a sample size of 140 HIV-patients allows to estimate the GMTs HPV type 6, 11, 16 and 18 with a power of 0.38, 0.82, 1 and 1, respectively (7, 19).

Due to difficulties in the recruitment of HIV patients without genital warts a recalculation of the sample size was done. With a total sample size of  $n=100$ , a majority of whom will have no history of HPV-lesions, we expect to be able to use the data of at least 80 patients for the analysis seroconversion of each HPV type under study. Seroconversion rates of 95-99% for HPV types 6, 11 and 16 can then be

estimated with a margin of error of  $\pm 4.8\%$  -  $2.2\%$ , and the anticipated seroconversion rate of 90% for HPV type 18 with a margin of error of  $\pm 6.6\%$ .

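### Section 3.5.6 claims more precision than the design assures: 80 evaluable HIV patients per type is not a floor, the SOT margin counts all 170 enrolled, and the symmetric HIV margins overstate the lower limit

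*Combined protocol and SAP*

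**What the plan says.** Section 3.5.6 justifies the sample size for seroconversion by precision alone.

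- **HIV.** With 100 enrolled, "we expect to be able to use the data of at least 80 patients for the analysis seroconversion of each HPV type under study". The margins that follow are ±4.8% to ±2.2% for rates of 95–99% (types 6, 11, 16) and ±6.6% for 90% (type 18).
- **SOT.** At an expected rate of 80%, "a sample size of 170 transplant patients allows to estimate the proportion of protected transplant patients with precision" of ±6%.

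The Rationale for Amendment 1 gives the background. Of the previous calculation for 140 HIV patients it says "This sample size calculation does not take in to account that patients might be seropositive to certain HPV-types at baseline". It reports that seroprevalence in earlier quadrivalent-vaccine studies "in HIV patients ranged from 13% to 45% for the different vaccine HPV-types". It widens entry in order to reach 100: "Enrolling patients with history of genital warts, who are most likely seropositive to HPV types 6 or 11", still add HPV-18 seronegative patients. It also notes that "clinical presentation of HPV infection does not necessarily implicate seropositivity to HPV".

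The primary analysis uses the type-specific per-protocol immunogenicity (PPI) sets of Section 3.5.4.1, for HIV and SOT alike. A subject must "Be seronegative to the appropriate HPV type at Day 1", have all three doses and both serum samples within the day ranges with evaluable results, and have no interfering deviation. Under Section 3.5.5.1, seroconversion "by 4 weeks after Dose 3, will be described with 95% CI"; no interval method is named.

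**The concern.** A floor of 80 out of 100 for every type allows at most 20% loss from all causes together. The cited seroprevalence alone can take more than twice that. No derivation of 80 is shown and no rate of other losses is stated. No seroprevalence is given for types 31, 33, 45, 52 and 58, which the quadrivalent-vaccine studies would not cover.

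The amendment recognised that ignoring baseline seropositivity was a fault in the HIV calculation. The SOT calculation has the same fault and was left as it was.

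For rates close to 100%, a single ± figure misplaces the interval. Its upper end can pass 100% and its lower end is too high. The lower limit is what a reader relies on when judging a vaccine response, and these margins are what the plan says the reduced sample delivers for its primary outcome.

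**Working it through.** **Inputs.** From Section 3.5.6: n = 170 at 80% (SOT); n = 80 of 100 at 90, 95 and 99% (HIV). From the Rationale for Amendment 1: baseline seroprevalence s of 13–45%. Confidence level 95%, z = 1.96. Rates of other loss are not in the documents; 5% and 10% (HIV) and 10% and 20% total (SOT) are assumptions.

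**1. The plan's margins**, from 1.96 × √(p(1−p)/n):

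- SOT: 1.96 × √(0.80 × 0.20/170) = 6.01 points (stated 6).
- HIV, n = 80: 6.57 at 90%, 4.78 at 95%, 2.18 at 99% (stated 6.6, 4.8, 2.2).

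All agree, so the plan used the symmetric normal form. At 99% the upper end is 99 + 2.18 = 101.2%.

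**2. Evaluable HIV patients per type**, n = 100 × (1 − s) × (1 − other loss):

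| s | no other loss | 5% | 10% |
|---|---|---|---|
| 13% | 87.0 | 82.7 | 78.3 |
| 45% | 55.0 | 52.3 | 49.5 |

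To keep 80, s must not exceed 1 − 0.80/(1 − other loss). This is 20.0%, 15.8% and 11.1% for other losses of 0, 5 and 10%; the last is below the lowest cited value of 13%. At s = 13% the break-even other loss is 1 − 80/87 = 8.0%. The binomial probability of at least 80 seronegatives among 100, with no other loss, is 0.98 at s = 13%, 0.56 at 20%, 0.02 at 30% and about 0 at 45%.

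Symmetric margins at n = 55 are ±7.9 (90%), ±5.8 (95%) and ±2.6 (99%).

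**3. Limits suited to rates near 100%.** Wilson limits are [p + z²/2n ± z√(p(1−p)/n + z²/4n²)] / (1 + z²/n):

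| Rate | Lower limit implied by the plan | Wilson, n = 87 | Wilson, n = 80 | Wilson, n = 55 |
|---|---|---|---|---|
| 90% | 83.4 | 81.9–94.7 | 81.5–94.8 | 79.3–95.5 |
| 95% | 90.2 | 88.2–98.0 | 87.8–98.0 | 85.8–98.4 |
| 99% | 96.8 | 94.0–99.8 | 93.7–99.8 | 91.7–99.9 |

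From unrounded values, the implied lower limits are too high by 1.9, 2.4 and 3.2 points at n = 80, and by 4.1, 4.5 and 5.1 points at n = 55. Clopper-Pearson limits agree at n = 80: the lower limit is 81.2 for 72/80, 87.7 for 76/80 and 93.2 for 79/80.

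**4. SOT at 80%.** A total loss of 10% (n = 153) gives ±6.3; 20% (n = 136) gives ±6.7. Applying the HIV range of 13–45% purely as an illustration (n about 148 to 94) gives ±6.4 to ±8.1. With n = 170 the Wilson interval is 73.4–85.3 against 74.0–86.0, so the interval form matters little for SOT.

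**The case against.** - **80 is an expectation and already allows for seropositivity.** The plan says it expects 80, on the footing that most patients have no history of HPV lesions, and it uses 80, not 100. The sentence admitting the omission concerns the old calculation for 140. All of this is true. But a floor for every type still needs a basis, and none is shown.
- **The 13–45% comes from other cohorts.** The 69 patients enrolled when the amendment was written had entered under criteria that screened out condylomata, so seroprevalence here may be lower than in those studies. This stands: 55–87 is what the cited range implies, not a forecast. It is, however, the only figure the documents offer. Patients with warts are added afterwards, which may raise seropositivity for types 6 and 11.
- **n = 55 is a worst case.** This stands. The documents do not say which type has 45%, so the n = 55 column should not be read as the HPV-18 result.
- **The SOT effect is small.** This stands. A 10% loss gives ±6.3, which still rounds to the stated figure.
- **Wilson mostly shifts the centre.** At n = 80 its half-width is 6.7 at 90% and 5.1 at 95%, close to the stated 6.6 and 4.8; only at 99% is it clearly wider, 3.1 against 2.2. This is correct about total width. The lower limit still falls by 1.9 to 3.2 points.
- **Nothing turns on it.** The plan sets no precision threshold, and the final intervals will use the actual numbers. This limits the severity, but the stated precision remains unsupported by the plan's own figures.

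**Conclusion.** The concern holds and should be fixed. The stated margins are arithmetically right for the numbers put in, but those numbers and the interval form are too favourable.

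- **HIV numbers.** 80 lies inside the range implied by the cited seroprevalence and is not its minimum. It fails for any type with seroprevalence above 20%, and fails even at 13% once other losses exceed 8.0%.
- **HIV limits.** The lower limits are overstated at n = 80 whatever the seroprevalence. The further drop at n = 55 depends on the upper end of a range from other cohorts.
- **SOT.** ±6% needs all 170 to be evaluable. The likely correction is under one point for a 10–20% loss, and its size rests wholly on that assumption.

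None of this undermines the feasibility of the trial or the choice of endpoint.

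**What to change.** In Section 3.5.6:

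1. Replace the floor of 80 with the expected evaluable number per type, 100 × (1 − baseline seropositivity) × (1 − other loss), with the loss rate stated. For the types the cited range covers this is about 55–87 before other losses. Use type-specific values if the cited studies give them.
2. Treat types 31, 33, 45, 52 and 58 in the same way, labelled as assumptions.
3. Replace the SOT basis of 170 with an expected evaluable number under a labelled assumption for total loss, with a range (for example 153 to 136, giving ±6.3 to ±6.7).
4. Give HIV precision as lower and upper Wilson limits at those numbers instead of one ± figure. Clopper-Pearson would also serve; name one.

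In Section 3.5.5.1, name the same interval for the seroconversion 95% CI.

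The cost is wording only: no extra patients, and no change to endpoint or analysis population. The stated precision becomes somewhat less favourable.

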### 3.5.7 Interim Analysis

No interim analysis is planned.

## 3.6 DEFINITION OF COMPLIANCE MEASURE

Compliance is defined in this study as receipt of all scheduled study vaccinations. To summarise compliance, the numbers of subjects who receive each vaccination will be tabulated. Compliance with the planned vaccination schedule (Day 1, Month 2, and Month 6) will be described by histograms of actual intervals between vaccinations relative to the expected interval in the CSR.

## 3.7 Labeling, Packaging, Storage, Dispensing, and Return of Clinical Supplies

### 3.7.1 Product Description

Investigational Medicinal Product (IMP) will be provided by MSD as summarized in

Table 7.

**Table 7: Investigational medicinal product**

Product name	Potency	Dosage Form/ Content s/ Route of Administration	Storage Conditions
GARDASIL®9 V503 (9-Valent HPV L1 VLP) Vaccine (Recombinant, adsorbed)	HPV Types (L1 protein) 6/11/16/18/31/33/45/52/58  30/40/60/40/20/20/20/20/20 mcg  Adsorbed on AAHS 500 mcg	Sterile suspension for intramuscular injection  1 dose (0.5 mL)  Shake well before use.	Store at 2.0 to 8.0°C  Do not freeze. Protect from light.
AAHS, Merck Aluminum Adjuvant (amorphous aluminum hydroxyphosphate sulfate); HPV, human papillomavirus; VLP, virus-like particle.			

GARDASIL®9 is available as a suspension for injection. It appears as a clear liquid with white precipitate.

### 3.7.2 Packaging Information

Supplies will be labelled in accordance with local regulatory requirements.

### 3.7.3 Clinical Supplies Disclosure

Not applicable. This study is open-label.

### 3.7.4 Shipment of Investigational Medicinal Product

The IMP will be shipped to the study site, refrigerated and stored at 2.0°C to 8.0°C following the guidelines on transport on commercial goods. Upon receipt at the study site, the vaccine should be removed from the outer secondary shipping box and placed immediately into the refrigerator.

Upon arrival of the shipment at the study site, the person responsible will verify that the content of the shipment corresponds to the order and that the products arrived in good condition. He/she will acknowledge receipt to MSD Belgium by email.

### 3.7.5 Storage and Handling Requirements

The clinical supplies storage area at the study site must be monitored by the site staff for temperature consistency with the acceptable storage temperature range specified in this protocol or in the product label attached to the protocol. Documentation of temperature monitoring should be maintained. Supplies should be stored in the original nested box with the lid closed to minimize exposure to light. If the refrigerator in which the study vaccine is stored deviates from the 2.0°C to 8.0°C range, study vaccinations should be suspended and MSD should be contacted immediately. Vaccine must NOT be frozen.

A daily refrigerator temperature log must be maintained at the study site. The refrigerator must be equipped with an appropriately calibrated min/max thermometer and/or circular chart temperature recorder. The temperature log will be reviewed by the investigator (or designee). An appropriate back up system (i.e., alarm or generator) and study site personnel telephone numbers should be in place in the event of a refrigerator failure.

In case of a cold chain break (i.e., if the temperature of the refrigerator is lower than 2.0°C or exceeds 8.0°C):

- The investigator (or designee) at the site should follow the current clinical complaint process to file an excursion
- The investigator (or designee) must wait for further instructions from MSD, as to whether or not the study vaccines can be used. The investigator is not allowed to use the study vaccines before getting MSD approval to do so.
- The cold chain break must be documented in the Investigator site file and the Trial Master File.

The IMP must be received by a designated person at the study site, handled and stored safely and properly, and kept in a secured location to which only the investigator and designated assistants have access. IMP is to be administered only in accordance with the protocol.

Any concerns raised about the manufacturing, packaging, labelling, or distribution of IMP supply which could potentially impact its suitability for use should be immediately reported to MSD. The IMP must be quarantined until the MSD's feed-back is received as to whether or not the vaccine can be used.

Unused study vaccines taken out from the stock at study site are considered to be unusable and cannot be returned to the stock. They must be quarantined and returned back to MSD as soon as possible.

### **3.7.6 Accountability of Investigational Medicinal Product**

For the accountability procedure, please refer to Guidelines for IMP Management on site.

### **3.7.7 Return of Investigational Medicinal Product**

All empty primary containers will be destroyed at the study site according to local regulations. Supplies will need to be returned to the depot of origin if destruction is not possible locally.

Empty boxes of study vaccines must be kept at study site to enable verification of the vaccine accountability and can be destroyed on site after study has been completed. The following should be returned to the distributor according to the procedures detailed in the Investigator Site File:

- Study vaccines unusable following a cold chain deviation, as soon as possible;
- Study vaccines expiring within the current month, immediately;
- Unused study vaccines which remain in stock at study site after the last administration to the last subject of the corresponding study site, after verification of vaccine accountability;
- Study vaccines concerned by a batch recall, immediately.

For the return procedure, please refer to Guidelines for IMP Management on site. The distributor will confirm the receipt of each study vaccine returned (at unit level).

## **3.8 Data Management**

Study data will be acquired via electronic format. As part of their responsibilities, the principal investigator or sub-investigator agree to maintain adequate source documents for the subjects treated as part of the research under this protocol. The principal investigator or sub-investigator agree to maintain source documentation (e.g., laboratory reports), to enter subject data into the individual subject's CRF as accurately as possible.

Each CRF will allow data entry by study site staff that can add and edit data, identify and resolve discrepancies, and view records. This system detection of discrepancies, enabling study site coordinators to resolve and manage discrepancies in a timely manner.

The electronic database will be password protected. A quality review of the data will be performed by the study site by an independent person through risk-based source data verification of essential data.

## **3.9 Study report**

A clinical study report will be provided in which the study results will be compared with historical controls.

## **4.0. ADMINISTRATIVE AND REGULATORY DETAILS**

### **4.1. Confidentiality**

#### **4.1.1. Confidentiality of Subject Records**

By signing this protocol, the investigator agrees that IRB/ERC, or regulatory authority representatives may consult and/or copy trial documents in order to verify worksheet/case report form data. By signing the consent form, the subject agrees to this process. If trial documents will be photocopied during the process of verifying worksheet/case report form information, the subject will be identified by unique code only; only serum samples will be transmitted to MSD, which will only have a unique code..

By signing this protocol, the investigator agrees to treat all subject data used and disclosed in connection with this trial in accordance with all applicable privacy laws, rules and regulations.

#### **4.1.2. Confidentiality of IRB/IEC Information**

The Sponsor is required to record the name and address of each IRB/IEC that reviews and approves this trial. The Sponsor, in collaboration with the relevant investigator is also required to document that each IRB/IEC meets regulatory and ICH GCP requirements by requesting and maintaining records of the names and qualifications of the IRB/IEC members and to make these records available for regulatory agency review upon request by those agencies.

### **4.2. Compliance with Law, Audit and Debarment**

By signing this protocol, the investigator agrees to conduct the trial in an efficient and diligent manner and in conformance with this protocol, ICH GCP guidelines, the EU Clinical Trial Directive (as it may be amended or superseded from time to time), the latest version of the Declaration of Helsinki ; and all applicable federal and local laws, rules and regulations relating to the conduct of the clinical trial.

The investigator also agrees to allow monitoring, audits, IRB/IEC review and regulatory authority inspection of trial-related documents and procedures and provide for direct access to all trial-related source data and documents.

The investigator agrees not to seek reimbursement from subjects, their insurance providers or from government programs for procedures included as part of the trial reimbursed to the investigator by the Sponsor.

The investigator shall prepare and maintain complete and accurate trial documentation in compliance with Good Clinical Practice standards and applicable federal and local laws, rules and regulations.

The investigator must maintain copies of all documentation and records relating to the conduct of the trial in compliance with all applicable legal and regulatory requirements. This documentation includes, but is not limited to, the protocol, worksheets/case report forms, advertising for subject participation, adverse event reports, subject source data, correspondence with regulatory authorities and IRBs/ERCs, consent forms, investigator's curricula vitae, monitor visit logs, laboratory reference ranges, laboratory

certification or quality control procedures and laboratory director curriculum vitae. By signing this protocol, the investigator agrees that documentation shall be retained at least 20 years the study was concluded.

ICH Good Clinical Practice guidelines recommend that the investigator inform the subject's primary physician about the subject's participation in the trial if the subject has a primary physician and if the subject agrees to the primary physician being informed.

The investigator will promptly inform Sponsor of any regulatory authority inspection conducted for this trial. Persons debarred from conducting or working on clinical trials by any court or regulatory authority will not be allowed to conduct or work on this trial. The investigator will immediately disclose in writing to the IRB/IEC if any person who is involved in conducting the trial is debarred or if any proceeding for debarment is pending or, to the best of the investigator's knowledge, threatened.

In addition, the investigator will review the trial report that summarizes the trial results and will describe the conduct and results of the trial [Clinical Study Report (CSR)] accurately to the best of his/her knowledge.

